PROTOCOL DOCUMENT FOR THE BREASTFEEDING OSTEOPATHIC MANUAL THERAPY STUDY (BROMS)

[name]
[name]
Adjunct Associate [name]
Associate [name]

Protocol for the Breastfeeding Osteopathic Manual Therapy Study

This Project Description provides the scientific and academic background and context for the research project 'Breastfeeding Osteopathic Manual Therapy Study (*BROMS*)'.

Summary:

This study is a two-armed, multi-centre, pragmatic, randomised clinical trial designed to examine the effect of osteopathic care (OMT) on breastfeeding dyads experiencing breastfeeding difficulty. The trial will be conducted in two stages: preliminary and full. Both stages have the same design.

The preliminary stage will pilot the design at a single clinic in Melbourne by recruiting 16 mother-infant dyads (MIDs) experiencing breastfeeding difficulty. The full stage will extend the pilot to multiple clinics across Melbourne and Canberra (See Appendix 1.1 – Clinic Consent Form).

Participants in both stages will be randomly allocated to one of two groups: international board-certified lactation consultant (IBCLC) - Standard care (Control) or IBCLC plus osteopathic intervention (OMT) (Experimental). The full stage will continue the pilot stage and see a further 54 MIDs (total N=70) experiencing breastfeeding difficulty randomly allocated to the same two groups. Recruitment for this stage will be from osteopathic clinics, maternal health centres and breastfeeding drop-in centres across metropolitan Melbourne and Canberra.

Each participant will undergo 4 weeks of intervention with a follow-up phone call one-month post-intervention.

The primary outcome of the study is change in infant breastfeeding function as measured by the Bristol Breastfeeding Assessment Tool (BBAT).

Secondary outcomes include maternal breastfeeding confidence, as measured by the Breastfeeding Self-efficacy Scale – Short form (BSES-SF) and changes in breastfeeding symptoms such as maternal breastfeeding-related pain, infant ability to latch and maintain latch to the breast and feeding noise at the breast measured using a series of visual analogue scales (VAS).

1. Study details

1.5 Background

Breastfeeding has been linked to short and long-term health benefits for infants and mothers.[1-6] Despite these benefits, breastfeeding is no longer considered a norm in many communities across the globe.[7] The World Health Organization (WHO) and the Australian Department of Health recommend breastfeeding for the first 6 months after birth and support maintaining the practice for up to 2 years with appropriate complementary feeding.[8-10]

Mothers can experience a range of physical symptoms associated with difficulty breastfeeding. These relate to infant latch, leakage, letdown, engorgement, nipple pain, cracked and bleeding nipples and nipple blistering.[11] In an attempt to manage such symptoms, a number of mothers are turning to manual therapy practitioners for help. In the UK, the number of infants taken to osteopaths annually has been estimated to be 61,000.[12] This corresponds to approximately 9% of all infants born in the

UK each year,[13] while an Australian study reported 48.7% of infants presenting to a chiropractic clinic did so for breastfeeding difficulties.[14] Despite an apparent high level of utilisation, evidence of the effectiveness of OMT care for treating breastfeeding difficulty remains unclear.

1.5.1 Musculoskeletal findings associated with breastfeeding difficulty

Key determinants of effective breastfeeding are latch, suck, swallow, and the respiratory actions of the infant at the breast [15, 16] where musculoskeletal dysfunction in an infant may affect the infant's ability to feed successfully from the breast. Musculoskeletal dysfunction such as congenital torticollis has been linked to breastfeeding difficulties [17]. One osteopathic publication identifies the most common musculoskeletal dysfunction found in infants with breastfeeding difficulties were found in the cranial, cervical and temporomandibular regions [18]. However, this association is based on anecdotal evidence and is yet to be tested under controlled settings.

1.5.2 Safety

Osteopathy has been used and documented in the management of breastfeeding difficulties [18-21]. No studies have reported on adverse events resulting from OMT care for infants with breastfeeding difficulty. While this may represent a failure to report, it could also suggest that manual therapy is a relatively low-risk care for this group of patients, a view that is supported in the literature. [22, 23]

A systematic review by Carnes et al (2017), concluded that the risk of adverse events associated with manual therapy that involved physical and/or manual contact with the infant for therapeutic intent was low (7 per 1000 infants exposed to manual therapy (n=1308)). Of the eight studies that reported on the presence of adverse events, three reported no adverse events, two reported adverse events following manual therapy while the other three reported adverse events in the non-manual therapy control groups. All reported adverse events reported in the above studies were non-serious in nature.

In our study, the treating osteopaths will be carefully selected, they will need to have over 10 years' experience and, have extensive training in paediatric care. This helps manage risks associated with inexperience.

In our study, adverse events will be monitored at every treatment session by the treating osteopath or IBCLC. This approach facilitates early detection, assists with mitigation, and improves management by reducing the risk of recurrence. Regarding the techniques used, the Osteopaths participating in this study are trained in low intensity, gentle techniques suitable for infants and children. High velocity or forceful techniques do not form part of osteopathic paediatric care and are not part of this study. This minimises the risk of iatrogenic injury.

All adverse events will be monitored at every treatment session by the treating osteopath or IBCLC. This approach facilitates early detection, assists with mitigation, and improves management by reducing the risk of recurrence.

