4.1.4 Trial design

All participants will require a pre-screen appointment to assess their eligibility to join the trial.

All participants will receive a maximum of two IBCLC face-to-face sessions and two IBCLC telehealth calls over a 4-week period. In addition to this, the IBCLC group will receive up to two additional telehealth consultations if required whereas the IBCLC + OMT group will receive up to three OMT consultations.

Outcome measures will be administered at baseline and again at weeks 4 and 8. At 8 weeks, all participants will receive a follow-up phone call/email from the trial coordinator, which will gather information on the breastfeeding status of the MID.

[figure not shown]

Figure 1: Flow chart

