10.1 Risk Management

The risks associated with participation in this study will be mitigated and managed along the following lines:

Physical harm to a member of a vulnerable population

In conjunction with the research team, the treating clinician (IBCLC or osteopath) will question parents about the occurrence of adverse events during the trial. If an adverse event requires additional medical care, the treating clinician will refer the mother and infant to a hospital or their GP, depending on which is the most appropriate course of action to take given the circumstances. The adverse event will be recorded and reported to the CI who will then take appropriate action.

Psychological harm to the mother

In conjunction with the research team, the treating clinician (IBCLC or osteopath) will monitor participating mothers for signs of post-natal depression (PND). If signs of PND become apparent, the mother will be referred to their GP for further assessment and management.

Familial distress

In conjunction with the research team, the treating clinician (IBCLC or osteopath) will monitor participating parents for signs of familial distress. If signs of familial distress become apparent, the parents will be referred to their GP for further assessment and management.

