12.0 Recruitment Duration and Study Duration

It is anticipated that the recruitment phase of the trial will be 12 months. If the target recruitment number is not reached in that time, there is provision to extend the recruitment period by a further 6

months. The entire project will run over a 2-year period (Figure 2). Each participant will be involved for a total of 8 weeks.

13.0 Participant time commitment:

The total time commitment for each participant is 330 or 360 minutes (6-6.5 hours) (See Table 1). We acknowledge that in some circumstances, there will be an inequality of 10% in the total time spent for each group. We believe this is acceptable given the nature of the trial.

	INTERVENTION	IBCLC (Minutes)	IBCLC/OMT (Minutes)
Week 0	Baseline Measurements (Face-to Face)/Paperwork (Online)	60	60
Week 1	IBCLC 1	60	60
Week 2	IBCLC 2	30	30
	OMT 1		60
Week 3	Up to 2 x 1/2-hour IBCLC Telehealth	60	
	Up to 2 x ¼ - hour IBCLC telehealth		30
	OMT 2		30
Week 4	Up to 2 x 1/2 - hour IBCLC Telehealth (as required)	60	
	OMT 3 (as required)		30
	Post Intervention paperwork (Online)	30	30
Week 8	Discharge paperwork - Follow up Phone call	30	30
	Total Minutes	330	360

Table 1: Participation for each group

- IBCLC 1 Initial Consultation with an IBCLC
- IBCLC 2 Follow-up Consultation with IBCLC
- OMT 1 Initial Consultation with an Osteopath
- OMT 2 & 3 Follow-up Consultation with Osteopath

Practitioners must also complete a 4-hour pre-trial training and a 1-hour Global Health Training Centre—Good Clinical Practice Course.

Participants will be followed up 1 month after finishing the intervention phase of the trial. At that follow-up they will be asked to complete the BSES-SF and VAS measures via email and participate in a short 5-minute telephone conversation with the trial coordinator about their current breastfeeding status.

If they are continuing to have difficulty breastfeeding and need further support, they will be referred to the Australian Breastfeeding Association where breastfeeding support counsellors are available free of charge.

15 Data Collection

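### Active adverse event enquiry is scheduled only at treatment sessions, which differ between arms in mode and end by week 4; weeks 5 to 8 rely on passive reporting

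*Protocol*

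**What the plan says.** Section 1.5.2 (Safety) states that "adverse events will be monitored at every treatment session by the treating osteopath or IBCLC". Section 10.1 (Risk Management) adds that, together with the research team, "the treating clinician (IBCLC or osteopath) will question parents about the occurrence of adverse events during the trial", without giving a schedule.

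Section 4.1.4 fixes the contacts. For both arms: "All participants will receive a maximum of two IBCLC face-to-face sessions and two IBCLC telehealth calls over a 4-week period". Beyond these, "the IBCLC group will receive up to two additional telehealth consultations if required whereas the IBCLC + OMT group will receive up to three OMT consultations". Table 1 (section 13.0) places all sessions in weeks 1 to 4 and marks the week 4 contacts in both arms as given only if required.

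Each participant is involved for 8 weeks (section 12.0). The text after Table 1 describes the week 8 follow-up: mothers complete the BSES-SF and VAS by email and "participate in a short 5-minute telephone conversation with the trial coordinator about their current breastfeeding status". Adverse events are not mentioned there.

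The adverse event text just before section 22 says that reports made by phone or email outside clinic time are managed by the CI, that the CI reviews medical records daily during the intervention phase, and that every event in the trial is recorded, related or not.

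**The concern.** The commitment is to record all events over the whole trial, but the procedure that elicits them stops with the last treatment session. For weeks 5 to 8, and after OMT 3 in particular, an event enters the record only if a mother volunteers it.

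Before that, mothers in the two arms are not asked in the same way. The enquiry is made by the treating clinician. The osteopath necessarily knows the allocation. The IBCLC gives telehealth calls whose length and number differ by arm, and sections 4.2 and 4.5 blind assessors to allocation but practitioners only to outcome results. One arm is asked mostly in person and the other mostly by telehealth.

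This matters because section 1.5.2 itself concedes that the lack of reported events in earlier studies may be a failure to report. Section 19 also asks the DSMB to advise on continuing, modifying or stopping for safety or ethical reasons. Events that were never asked about cannot be recovered in the analysis.

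**Working it through.** **The plan's own figure.** Table 1 by arm:
- Control: 60 + 60 + 30 + 60 + 60 + 30 + 30 = 330 minutes.
- OMT: 60 + 60 + 30 + 60 + 30 + 30 + 30 + 30 + 30 = 360 minutes.

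Both totals are reproduced. The difference is 30/330 = 9.1%, which the protocol calls 10%. That figure is total participant time and does not show the mode of contact.

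**Clinician contacts per dyad** (section 4.1.4 and Table 1):

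| | Control | OMT |
|---|---|---|
| Face-to-face, maximum | 2 | 2 + 3 = 5 |
| Telehealth, maximum | 2 + 2 = 4 | 2 |
| All sessions, maximum | 6 | 7 |
| All sessions, week 4 as-required contacts unused | 4 | 6 |
| Face-to-face minutes | 60 + 30 = 90 | 60 + 30 + 60 + 30 + 30 = 210 |
| Telehealth minutes | 60 + 60 = 120 | 30 |

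With 70/2 = 35 dyads per arm, the maximum number of face-to-face enquiries is 35 × 5 = 175 against 35 × 2 = 70. For sessions of any kind it is 35 × 7 = 245 against 35 × 6 = 210.

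**Time without scheduled enquiry.** The last possible session is in week 4, so 4 of 8 weeks (50%) have none in either arm. If the as-required contacts are not used, the last session is in week 3 and the gap starts a week earlier. Of up to 35 × 3 = 105 OMT sessions, up to 35 (one third) are OMT 3, with no scheduled later session.

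**How much the contact pattern could matter.** The protocol gives no detection rate, so this is illustration only. Suppose the true risk is the same in both arms, detection is independent across contacts, and the event is present throughout. Let the assumed detection chance be f per face-to-face contact and t per telehealth contact. Then P(detected) = 1 − (1 − f)^(face-to-face contacts) × (1 − t)^(telehealth contacts).

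| Assumption | Control | OMT | Ratio |
|---|---|---|---|
| Maximum sessions, f = t = 0.1 | 0.469 | 0.522 | 1.11 |
| Maximum sessions, f = t = 0.5 | 0.984 | 0.992 | 1.01 |
| Maximum sessions, f = 0.1, t = 0.05 | 0.340 | 0.467 | 1.37 |
| Maximum sessions, f = 0.5, t = 0.25 | 0.921 | 0.982 | 1.07 |
| As-required unused, f = 0.1, t = 0.05 | 0.269 | 0.408 | 1.52 |
| As-required unused, f = 0.5, t = 0.25 | 0.859 | 0.965 | 1.12 |

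The model leaves out timing. An event caused by OMT cannot be found before OMT 1 in week 2, and one that follows OMT 3 has no later session at which to be found.

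**Precision.** At the 7 per 1000 cited in section 1.5.2, 35 OMT infants give 35 × 0.007 = 0.245 expected events, and the chance of at least one is 1 − 0.993^35 = 0.22. That figure concerns manual therapy; the protocol gives no rate for the unrelated events that it also intends to record.

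**The case against.** A reader might infer that the trial's safety comparison is biased and that events after the last session are lost. The documents support neither.

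- **No such comparison is specified.** Adverse events are listed as collected data (section 4.6), but not among the outcomes (4.4), the hypotheses (2.2) or the described analyses (5.0). Section 1.5.2 presents session monitoring as early detection and mitigation. This stands: the text shows a risk to the data, not a biased result.
- **Other routes exist.** Section 10.1 speaks of questioning during the trial, not only at sessions, and phone or email reports are handled. This stands in part: later events can be captured. But section 10.1 names the treating clinician, who has no scheduled contact after week 4, and the phone and email route waits for the mother to report.
- **The forms are not shown.** The adverse event form (Appendix 12.1) and the week 4 and week 8 paperwork may contain an adverse event item. Table 1 allots 30 minutes at week 8, of which the call takes 5. This stands, and the fix allows for it.
- **A large detection gap is not supported.** Counting only face-to-face contacts at an assumed 0.1 gives 1 − 0.9^5 = 41% against 1 − 0.9^2 = 19%. That sets telehealth detection to zero, whereas section 1.5.2 covers every treatment session. With all contacts equal, the same 0.1 gives 52% against 47%.
- **The direction is not settled.** More face-to-face contact favours detection in the OMT arm, while missed events after OMT 3 work the other way. The gap in weeks 5 to 8 applies to both arms.

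**Conclusion.** The point holds as a risk of incomplete and differential ascertainment. Two parts rest on the text alone: no active enquiry is described for weeks 5 to 8, half of each dyad's participation, despite the commitment to record all events; and the sessions at which mothers are asked differ by arm, mainly in mode (up to 5 against 2 face-to-face) and slightly in number (up to 7 against 6).

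The size of any between-arm effect is unknown. The illustrative ratios of 1.01 to 1.52 depend on assumed detection rates and on an event being present at every contact. At the cited 7 per 1000, any comparison in a trial of this size would be very imprecise however mothers were asked. The gain from a change is therefore in completeness and like-for-like capture; it would not make the trial able to establish low or excess risk. The conclusion would weaken if the forms that are not shown already ask both arms about adverse events. This is a matter of data collection and cannot be left to an analysis plan.

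**What to change.** Add one identical, neutrally worded set of adverse event questions for every mother in both arms to the week 4 online paperwork and to the week 8 form or call. If the existing forms already contain such questions, say so in sections 1.5.2 and 13.0.

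Route the answers to the trial coordinator or the CI, not to the blinded assessor, at least until the outcome scores are recorded, since a mother's answer may mention the osteopath and reveal the allocation. Base any between-arm summary of adverse events on these uniform answers, and list session-reported and spontaneously reported events separately. Monitoring at sessions continues as planned.

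The cost is a few items on forms or a call that every mother already receives, and a short protocol amendment. It needs no extra visits. Mothers remain unblinded, so uniform questions make the enquiry equal but do not remove differences in what mothers choose to report.

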1.5.3 Conclusion

The literature on the use of manual therapy intervention in the management of infants experiencing breastfeeding difficulty highlights a growing body of evidence supporting its use, with the majority of studies involving osteopathic care. Osteopathic manual therapy appears to be relatively safe for this group of infants. Despite limited evidence, there is an increasing demand for osteopathic services

among mothers with breastfeeding difficulty. Further research is required before any claim about the benefits of manual therapy intervention for infant breastfeeding difficulty can be relied upon.

1.6 Rationale and Justification for the Research

Lactation consultants, physiologists, speech pathologists and clinicians have extensively studied the biomechanics, fluid dynamics and mechanism of infant sucking while breastfeeding. [24-26] International Board-Certified Lactation Consultants (IBCLCs) are trained to assess difficulties, correct positioning, provide emotional support to mothers and help babies improve the suck, swallow and respiration behavioural sequence. However, these professionals often look for further assistance when biomechanical sucking difficulties persist in infants despite their advice [20, 27, 28] Osteopathy has been used and documented by some to be an additional help to breastfed infants in addition to IBCLC care.[21, 29] More research is needed to explore the clinical partnership of osteopathic care and IBCLC care for infants with breastfeeding difficulties.

1.7 Gaps in the research

- The effectiveness of OMT for infants with breastfeeding issues remains unclear
- Identification of the possible anatomical musculoskeletal structures involved in breastfeeding dysfunction is yet to be determined.
- The benefits of combining IBCLC with osteopathic care are unknown.

2. Aim of Research

The aim of this project is to investigate the efficacy of OMT intervention designed to address musculoskeletal dysfunction in the infant with breastfeeding difficulty.

2.1 Research questions:

This research aims to answer the following research questions:

1. Does OMT intervention deliver additional improvements in breastfeeding compared to standard care (IBCLC) in infants with breastfeeding difficulty?
2. Does OMT intervention deliver additional improvements in breastfeeding mechanical function compared to standard care (IBCLC) in infants with breastfeeding difficulty?
3. Does OMT intervention deliver additional improvements in maternal breastfeeding confidence compared to standard care (IBCLC) in infants with breastfeeding difficulty?

2.2 Research Hypotheses:

This study aims to test the following research hypotheses:

1. OMT intervention to the infant improves breastfeeding more than standard care (IBCLC) in infants with breastfeeding difficulty.
2. OMT intervention to the infant improves breastfeeding mechanical function more than standard care (IBCLC) in infants with breastfeeding difficulty.

2.3 Expected outcomes

We expect that infants receiving OMT intervention designed to address musculoskeletal dysfunction will have greater improvements in breastfeeding and maternal confidence in breastfeeding compared to standard care (IBCLC). We also expect that infant musculoskeletal dysfunction will present in the cranial, facial and cervical regions more than the rest of the body.

3.0 Project Design

3.1 Research Setting

Private osteopathic clinics across metropolitan Melbourne and Canberra.

3.2 Physical Sites

The study will be conducted in 3-5 private osteopathic clinics across metropolitan Melbourne and Canberra. (Both IBCLC and OMT intervention will occur at participating osteopathic clinics. All participating clinicians will be provided with an information sheet (Appendix 2.1) and asked to complete a practitioner consent form. (Appendix 3.1).

4.0 Methodological approach

This study is a two-armed, multi-centre, pragmatic, randomised clinical trial designed to examine the effect of osteopathic care (OMT) on breastfeeding MIDs experiencing breastfeeding difficulty. The trial will recruit 70 MIDs and be conducted in two stages: a preliminary stage leading to the full stage. Both stages have the same design (see Figure 1). Stage 1 (preliminary) is designed to pilot test the design and will involve 16 MIDs randomly allocated to one of the two groups. This will be followed by stage 2 (full stage) involving 54 MIDs randomly allocated to the same two groups.

4.1 Participants

Stage 1 (preliminary):

A total of N=16 MIDs experiencing breastfeeding difficulty will be randomly allocated to one of two equal groups.

Group 1: IBCLC

Group 2: IBCLC + OMT

There will be a two-week pause in the study once Stage 1 is complete to provide time for the researchers to review the trial's processes and procedures and to make any necessary minor modifications to the protocol. The trial will then proceed to Stage 2.

Stage 2 (full):

A total N=54 MIDs experiencing breastfeeding difficulty will be randomly allocated to one of the same two groups.

Group 1: IBCLC

Group 2: IBCLC + OMT

Once allocated to a group, participants may not switch groups.

